6.1.1.2.2 Assessment of Causality

The investigator's assessment of an AE's relationship to the IP is part of the documentation process, but it is not a factor in determining what is or is not reported in the study. If there is any doubt as to whether a clinical observation is an AE, the event should be reported.

The relationship or association of the IP in causing or contributing to the AE will be characterized using the following classification and criteria:

YES: There is a reasonable possibility that the IP contributed to the AE.

NO: There is no reasonable possibility that the AE is causally related to the administration of IP. There are other, more likely causes and administration of IP is not suspected to have contributed to the AE.

6.1.1.3 Reporting Adverse Events

All AEs reported or observed during the study will be recorded on the AE page in the eCRF. Information to be collected includes, but is not limited to, the following:

- Event term
- Investigator-specified assessment of severity and causality to IP
- Seriousness/grade
- Time of onset of the event
- Time of resolution of the event
- Any required treatment or evaluations
- Outcome

Adverse events resulting from concurrent illnesses, reactions to concurrent illnesses, reactions to concurrent medications, or progression of disease states must also be reported. All AEs will be followed to adequate resolution. MedDRA will be used to code all AEs.

Any medical condition that is present at the time that the participant is screened but does not deteriorate should not be reported as an AE. However, if it deteriorates at any time during the study, it should be recorded as an AE.

6.1.1.3.1 Reporting Serious Adverse Events and Adverse Events of Special Interest

Any AE that meets SAE criteria (Section 6.1.1.1.2) must be reported to PPD Pharmacovigilance within 24 hours after site personnel first learn of the event. Events should be captured electronically in the EDC system; however, if the EDC is unavailable, a backup paper option is available and this form can be faxed to the fax number listed below.

SAE [contact] [contact]

Any AE that meets AESI criteria (Section 6.1.1.1.4) must be reported to PPD Pharmacovigilance within 24 hours after site personnel first learn of the event.

If the EDC is unavailable and a faxed form is used to report an SAE or AESI, the site should update the EDC with exactly the same information reported on paper (by fax) as soon as possible after the EDC becomes available again.

The sponsor has a legal responsibility to notify both the local regulatory authority and other regulatory agencies about the safety of an IP under clinical investigation. The sponsor will comply with country-specific regulatory requirements relating to safety reporting to the regulatory authority, IRB/IEC, and investigators.

An investigator who receives an investigator safety report describing an SAE or other specific safety information from the sponsor will review and then file it as appropriate and will notify the IRB/IEC according to local requirements.

6.1.1.3.2 Reporting Suspected Unexpected Serious Adverse Reactions

The sponsor will promptly evaluate all SUSARs against cumulative product experience to identify and expeditiously communicate possible new safety findings to investigators, IRB/IECs, and applicable health authorities based on applicable legislation.

Reporting requirements will also be based on the investigator's assessment of causality and seriousness, with allowance for upgrading by the sponsor as needed.

6.1.1.4 Follow-Up of Participants Reporting Adverse Events

All AEs must be reported in detail on the appropriate page in the eCRF and followed to satisfactory resolution, until the investigator deems the event to be chronic or not clinically significant, the event is considered to be stable, or the participant is lost to follow-up.

6.1.1.5 eDiary

An eDiary will be used after study vaccination to record solicited local injection site and systemic AEs, body temperature, and any concomitant medications during 7 days after study vaccination (Days 1 to 7) for reactogenicity assessment. Study site personnel will instruct the participants on use of the eDiary. The site staff will review the eDiary data at Day 8.

Participants will be instructed to contact the study site as needed at any time point during the study with safety concerns. Any AE that meets SAE criteria (Section 6.1.1.1.2) must be

13 Jun 2022

reported to PPD Pharmacovigilance immediately (ie, within 24 hours) after site personnel first learn of the event (Section 6.1.1.3.1).

6.1.2 Clinical Safety Laboratory Assessments

The following laboratory assessments will be performed at the time points specified in the SOE (Table 13-1):

Hematology: Basophils, eosinophils, erythrocytes (red blood cells), hemoglobin,

leukocytes (white blood cells), lymphocytes, monocytes,

neutrophils, and platelets

Chemistry: Bilirubin (total and direct), alkaline phosphatase, alanine

aminotransferase, aspartate aminotransferase, blood urea nitrogen,

creatinine, and uric acid

SARS-CoV-2: • SARS-CoV-2 serology (Ab), which will include S and N protein

for prevaccination timepoints and N protein for postvaccination

timepoints to monitor for undetected SARS-CoV-2 infections

• SARS-CoV-2 RT-PCR (nasal swab)

HIV/HBV/HCV • Hepatitis B surface antigen test

• HIV 4th generation antigen/Ab test

• Anti-HCV test

Other analyses: Female participants of childbearing potential:

β-human chorionic gonadotropin (serum test at Screening; urine

test at additional time points)

Serum FSH, to confirm postmenopausal status (Section 13.2)

The clinical safety laboratory assessments will be performed by a local or central laboratory as detailed in the Laboratory Manual. Screening laboratory tests and SARS-CoV-2 RT-PCR may be repeated once for enrollment requirements.

The investigator must review the laboratory reports, document this review, and record any clinically relevant changes occurring during the study. If the laboratory reports are not transferred electronically, the values must be filed with the source information (including reference ranges). Any clinically relevant laboratory results should be reported as an AE or SAE, as appropriate, using the AE intensity grading (Section 6.1.1.2.1).

All laboratory tests with values considered clinically significantly abnormal during participation in the study should be repeated until the values return to normal or baseline or are no longer considered clinically significant by the investigator or medical monitor. If such values do not return to normal/baseline within a period of time judged reasonable by the investigator, the etiology should be identified, and the sponsor notified.

All protocol-required laboratory assessments must be conducted in accordance with the Laboratory Manual. If laboratory values from nonprotocol-specified laboratory assessments performed at the local study site laboratory require a change in participant management or are considered clinically significant by the investigator, then the results must be recorded in the eCRF.

6.1.3 Physical Examinations

A complete physical examination including height and weight will be performed at Screening as indicated in the SOE (Table 13-1). Symptom-directed physical examinations will be performed as clinically indicated at subsequent visits.

6.1.4 Vital Signs

Vital sign measurements will be performed at the time points indicated in the SOE (Table 13-1). Vital signs will be measured in a sitting position after at least 5 minutes of rest and will include temperature, pulse, respiration rate, oxygen saturation by pulse oximetry, and systolic and diastolic blood pressure. For participants who have an abnormal blood pressure reading at Screening, blood pressure measurement may be repeated and the blood pressure measurement for eligibility may be based on an average of up to 3 blood pressure measurements, to better assess whether known hypertension is well controlled or to evaluate for undiagnosed hypertension. These assessments can be made on separate visits during the screening period to provide more comprehensive sampling. Self-reported baseline measurements documented in a personal log or from medical records taken on consecutive

days in the week before the screening visit can also be accepted, subject to the investigator's discretion. Vital sign measurements should be collected before and after study vaccination on Day 1. Vital sign measurements should also be performed before any scheduled blood collection. Per standard clinical practice, vital sign measurements may be repeated per investigator discretion.

Body temperature will be measured throughout the study. Participants who are febrile (temperature $\geq 38.0^{\circ}$ C or $\geq 100.4^{\circ}$ F) before study vaccination should be rescheduled for study vaccination within the relevant window period of Screening.

6.1.5 Sentinel Participant Safety Follow-up Call

A safety follow-up telephone call to each sentinel participant in each dose group will be performed on Day 2 (at least 20 hours postvaccination). Vaccination of the next sentinel participant will proceed, provided the safety was acceptable for the prior sentinel(s) per investigator's assessment.

6.2 Pregnancy Reporting

Any pregnancy that occurs during study participation must be reported using the PPD paper pregnancy report form (Section 13.2) faxed to the same fax number as may be used for backup SAE reports (Section 6.1.1.3.1). To ensure participant safety, site personnel must report each pregnancy to PPD within 24 hours of learning of its occurrence. The pregnancy must be followed to determine outcome (including spontaneous miscarriage, elective termination, normal birth, or congenital abnormality) and status of mother and child, even if the participant was discontinued from the study. Pregnancy complications and elective terminations for medical reasons must be reported as an AE or SAE. Spontaneous miscarriages must be reported as an SAE.

Any SAE occurring in association with a pregnancy, brought to the investigator's attention after the participant has completed the study, and considered by the investigator as possibly related to the study vaccine, must be promptly reported to PPD as described in Section 6.1.1.3.1.

6.3 Pharmacokinetics

Pharmacokinetics will not be assessed in this study.

6.4 Pharmacodynamics and Biomarkers

Pharmacodynamics and biomarkers will not be assessed in this study.

6.5 Immunogenicity Assessments

Immunogenicity evaluations will be performed at sponsor designated laboratories as detailed in the Laboratory Manual.

Blood samples will be collected to evaluate vaccine-induced neutralizing and binding (IgG) Ab levels and cell-mediated immunity as indicated in the SOE (Table 13-1). On Day 1, the immunogenicity sample should be collected *before* study vaccine administration.

Neutralizing Ab levels against pseudovirus bearing spike from SARS-CoV-2 WT, and potentially pseudovirus bearing spike protein from other variants will be measured. Binding Ab IgG levels against SARS-CoV-2 S protein, RBD, N protein (from WT), and SARS-CoV-2 spike antigens (from other variants) will be measured. Antispike (from WT and potentially other variants) T-cell responses will be explored.

At a subset of study sites, PBMC samples will be collected and assessed by ICS assay (Table 13-1) to evaluate, but not limited to, antispike specific T-cell profiles. Additional T-cell parameters may be evaluated.

6.6 SARS-CoV-2 and COVID-19 Disease Assessment and Definitions

Vaccine efficacy will not be evaluated in this study, but all virologically confirmed SARS-CoV-2 infections should be reported by the participant and documented as clinical events as well as AESIs (Section 6.1.1.1.4). Any available isolate genotyping results will also be requested. Participants will be instructed to inform the investigator in the event of a positive SARS-CoV-2 diagnostic test. Clinical serology testing, including N protein, will be performed at Screening, Day 1, Day 85, and Day 180 to monitor for undetected SARS-CoV-2 infections. A nasal (nasopharyngeal or mid-turbinate) swab sample is scheduled for SARS-CoV-2 RT-PCR testing at Screening and Day 1. The screening sampling and SARS-CoV-2 RT-PCR testing must be performed within the 7 days before Day 1.

All participants with suspected COVID-19 are required to have an unscheduled visit for suspected COVID-19. At this visit, participants will undergo the following assessments:

- Medical history
- SARS-CoV-2 RT-PCR (nasal swab [nasopharyngeal or mid-turbinate])
- Physical examination
- Vital sign measurements
- Review of adverse events
- Concomitant medication/vaccination

All participants with confirmed COVID-19 are required to have an unscheduled COVID-19 convalescent visit. At this visit, participants will undergo the following assessments:

- Medical history
- Physical examination
- Vital sign measurements
- COVID-19 evaluation
- Review of adverse events
- Concomitant medication/vaccination

To complete the COVID-19 evaluation, the investigator will review the history of the participants, including medical records to define the severity of COVID-19. Any virologically confirmed cases of SARS-CoV-2 infection or COVID-19 during the study will be assigned one of the following definitions:

Asymptomatic	Virologically confirmed SARS-CoV-2 by RT-PCR or N protein
SARS-CoV-2	seroconversion without any of the following symptoms: fever or
infection:	chills, cough, shortness of breath or difficulty breathing, fatigue,
	muscle or body aches, headache, new loss of taste or smell, sore

throat, congestion or runny nose, nausea or vomiting, diarrhea

taste or smell, sore throat, congestion or runny nose, nausea or

Symptomatic Virologically confirmed by RT-PCR and include one or more of the COVID-19: following: fever or chills, cough, shortness of breath or difficulty breathing, fatigue, muscle or body aches, headache, new loss of

vomiting, diarrhea

13 Jun 2022

Severe COVID-19: Laboratory-confirmed SARS-CoV-2 infection with any of the following:

- Clinical signs at rest indicative of severe systemic illness (respiratory rate ≥30 per minute, heart rate ≥125 per minute, blood oxygen saturation ≤93% on room air at sea level or partial pressure of oxygen/fraction of inspired oxygen <300 mmHg)
- Respiratory failure (defined as needing high-flow oxygen, noninvasive ventilation, mechanical ventilation, or extracorporeal membrane oxygenation)
- Evidence of shock (systolic blood pressure <90 mmHg, diastolic blood pressure <60 mmHg, or requiring vasopressors)
- Significant acute renal, hepatic, or neurologic dysfunction
- Admission to an intensive care unit
- Death

The genetic sequence of the spike-encoding gene or the genome of SARS-CoV-2 strains will also be evaluated in relation to the vaccine sequence, when available.

6.7 Genetics

Human genetics will not be assessed in this study.

13 Jun 2022

CV2CoV mRNA Vaccine

7 Statistical Considerations

Analyses will be performed by treatment group combining the younger and older adult participants together, unless specified otherwise. Subanalyses may be performed within each age group. For categorical variables, frequencies, and percentages will be presented. Continuous variables will be summarized using descriptive statistics (number of participants, mean, median, standard deviation, minimum, and maximum).

7.1 Statistical Hypothesis

There is no hypothesis testing in this study; where statistical methods are applied, the emphasis will be on estimation with 95% CIs.

7.2 Sample Size Determination

The sample size is based on clinical considerations to inform dose regimen decisions for continued clinical development.

Approximately 180 participants will be enrolled in this Phase 1 study, with 6 dose-level cohorts each comprising 2 age groups. With 30 participants in each cohort, there is a 78.5% probability to observe at least 1 AE if the incidence rate is 5% and a 95.8% probability to observe at least 1 AE if the incidence rate is 10%. With 30 participants in each cohort, a 10% unevaluable rate for immunogenicity results, and a standard deviation of 0.45 for log₁₀-transformed increase from Day 1, the ratio of the upper limit of a 2-sided 95% CI and the point estimate of GMI is 1.5.

7.3 Analysis Sets

The following analysis sets will be used in the statistical analyses.

- Enrolled Set: All participants who have a signed ICF and were assigned to a group, vaccinated, or had an immunogenicity blood draw.
- Per Protocol Set: The PP set includes all eligible participants who received a dose of study intervention IP per protocol and who have values for predose and Day 29 neutralizing Ab titers against pseudovirus bearing S protein from Results from a blood sample deviating from the dosing or blood sampling schedule (Table 13-1) and results from a blood sample after intercurrent conditions that may

interfere with immunogenicity (eg, virologically confirmed SARS-CoV-2 infections or immunosuppressive or immunodeficient conditions) or from participants who received COVID-19 vaccination within 29 days postvaccination will be excluded from the PP set. The analysis will be done according to the dose that participants received at Day 1. The PP set will be used for the immunogenicity analyses.

• Safety Set: All participants who received any IP. All analyses using the Safety Set will group participants according to the study vaccine actually received. The Safety Set will be used for safety analyses.

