5.8.2 Allowed Concomitant Therapy

Any concomitant medication deemed necessary for the welfare of the participant during the study may be given at the discretion of the investigator. However, it is the responsibility of the investigator to ensure that details regarding the medication are recorded in full in the eCRF.

The following concomitant therapies are allowed during the study:

- Acetaminophen/paracetamol
- Contraception, as described in Appendix 13.2
- Low-dose topical, ophthalmic, inhaled, and intranasal steroid preparations
- Local intra-articular steroids that are expected to remain localized in the joint space in which they are administered
- Inactivated influenza vaccines are allowed if received at least 14 days before or after study vaccination. Note: If other nonstudy vaccines are received during the study, participants may continue to complete the remaining study assessments. Any impact on the immunogenicity data will be addressed in the data analysis.

 Participants may take concomitant medications for management of medically stable chronic conditions as long as the medication and medical conditions are not exclusionary (Section 4.1.2)

Participants will be allowed to receive a booster dose of a licensed or authorized (conditional regulatory approvals, including emergency use authorizations are acceptable) COVID-19 vaccine, per national recommendations, if received after the Day 29 visit.

No concomitant medications will be provided by the sponsor or PPD.

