13.1 Appendix 1: Schedule of Events

Table 13-1 Schedule of Events

	Screening	D1	D2 ^a	D8	D15	D29	D85	D180 (EOS)	Early Termination Visit	Visit for Suspected COVID-19 ^b	Unscheduled COVID-19 Convalescent Visit ^c
Window	D–14 to –1	0	NA	±1	±3	±3	±5	±7	±7	NA	NA
Visit	1	2	NA	3	4	5	6	7	7	NA	NA
Informed consent	X										
Inclusion/exclusion	X										
Reassess study vaccine eligibility ^d		X									
Demographics	X										
Medical history (including vaccination history)	X								X	X	X
Treatment assignment		X									
Pregnancy test ^e	X	X									
Clinical SARS-CoV-2 serology ^f	X	X					X	X	X		
SARS-CoV-2 RT-PCR (nasal	X	X								X	
swab) ^g	Λ										
Physical examination ^h	X	X		X	X	X	X	X	X	X	X
Vital sign measurements ⁱ	X	X		X	X	X	X	X	X	X	X
Clinical safety laboratory tests ^j	X	X		X							
Blood sample for binding IgGf, k		X		X	X	X^{i}	X	X	X		
Blood sample for neutralization ^{f, k}		X		X	X	Xi	X	X	X		
Blood for PBMC preparation for ICS (subset of participants)		X			X						
Vaccine administration		X									
COVID-19 evaluation ^c											X ^l
Initiate eDiary for solicited AEs		X									
Site staff review of eDiary	İ		X	X							
Adverse events ^m	X	X	X	X	X	X	X	X	X	X	X
Concomitant medication/vaccination	X	X	X	X	X	X	X	X	X	X	X

Note: Due to the ongoing pandemic, safety follow-up visits may be completed via televisits, as permitted by country regulations. In-person visits should be maintained in the study unless there is a public health emergency limiting access to study sites. During such an emergency or extenuating circumstance, televisits can be employed to keep personal access to subjects and ascertain their safety at a high level.

Protocol 217741 (CV2 SARS-COV2-002 BST) Amendment 2

13 Jun 2022

- a. A safety follow-up telephone call to each sentinel participant will be performed on Day 2 prior to the vaccination of the next participant.
- b. Required for participants with suspected COVID-19.
- c. Required for participants with confirmed COVID-19.

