3.4. Overdose Management

An overdose is any dose of study vaccine given to a participant that exceeds the planned dose for an individual within a given dose group.

There is no specific treatment recommended for an overdose. Overdose itself is not to be reported as an AE, however, any AEs associated with the overdose will be analyzed as relevant AEs/SAEs. Overdose participants will be included in the Safety Set and excluded from Per Protocol (PP) Set.

4. General Statistical Considerations

Participants will be identified in the listings by the participant identification number concatenated with the site number. Data will be displayed in all listings sorted by age group, dose group and participant number.

Continuous data will be described using descriptive statistics (n, mean, standard deviation, median, minimum, and maximum). **Categorical data** will be described using the participant count and percentage for each category.

For the **summary statistics** of all numerical variables unless otherwise specified, mean, confidence interval, median, standard deviation, minimum and maximum will be displayed.

A row denoted "Missing" will be included in count tabulations where specified on the shells to account for dropouts and missing values.

There is no formal hypothesis testing in this study where statistical methods are applied; the emphasis will be on estimation with 2-sided 95% CIs.

The denominator for all percentages will be the number of participants with non-missing values of corresponding parameter in that treatment within the analysis population of interest, unless otherwise specified.

A table, figure, or listing is to be generated for any required item even where no data is available or reported. In such cases, the outputs will state: "**No Data Reported**". This will confirm to the health authorities that all data for the tables, figures, listings, and narratives are accounted for.

If a participant has no data they will be excluded from the specific output.

Baseline will be defined as the last non-missing evaluation prior to study vaccine administration, unless otherwise specified.

Study day will be calculated as follows:

- a) study day prior to the injection will be calculated as: date of assessment date of the injection
- b) study day on or after the date of the injection will be calculated as: date of assessment date of the injection + 1

For Safety assessment of AEs, the intervals will be calculated as follow

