4.3.2. Per Protocol Set

The Per Protocol (PP) Set will include all eligible participants who received a dose of study intervention IP as per protocol and who have values for predose and Day 29 neutralizing Ab titers against pseudovirus bearing S protein from ^{CCI} Results from a blood sample deviating from the dosing or blood sampling schedule (Appendix 15.1) and results from a blood sample after intercurrent conditions that may interfere with immunogenicity (eg, virologically confirmed SARS-CoV-2 infections or immunodeficient conditions) or from participants who received COVID-19 vaccination within 29 days postvaccination will be excluded from the PP Set. The analysis will be done according to the dose that participants received at Day 1.

The PP Set will be used for the analysis of immunogenicity, demography and the analysis of PBMC subset.

Significant protocol deviations will be reviewed and may lead to exclusion from the PP Set.

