5.2. Protocol Deviations

Major protocol deviations are a subset of protocol deviations that may significantly impact the completeness, accuracy, or reliability of the study data or that may significantly affect a participant's rights, safety, or well-being. Major protocol deviations rules will be developed and finalized before database lock.

Major protocol deviations include, but are not limited to, the following:

- Study vaccine not administered at all
- Invalid/missing informed consent
- Fraudulent data
- Administration of concomitant vaccine(s) forbidden in the protocol
- Participants got vaccinated but not as per protocol
- Vaccine storage temperature deviation which is not accepted by quality
- Expired vaccine administered
- Ineligible participant
- Administration of any medication forbidden by the protocol
- Participants did not comply with blood sample schedule
- Serological results not available pre- or post-vaccination for at least neutralizing Abs against pseudovirus bearing S protein from
- Serological results available but results unreliable (e.g. wrong blood sample management)

The number of participants with major protocol deviations will be summarized by dose group. Major protocol deviations will be listed with date of occurrence, deviation description, and analysis set from which participant is excluded. The major protocol deviation summary will be based on the Safety Set.

The major protocol deviations will be listed by age group, dose group, participant number and will be reported in the CSR.

6. Demographics and Baseline Characteristics

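### Minor: the Per Protocol rule can drop a participant's pre-booster titers although Protocol 5.8.2 allowed the booster

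*Protocol*

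**What the plan says.** **Who leaves the Per Protocol (PP) Set.** Protocol 7.3 treats two kinds of event in one sentence. For intercurrent conditions such as confirmed infection, it removes results from samples taken after the event. For non-study COVID-19 vaccination, it removes results from participants who "received COVID-19 vaccination within 29 days postvaccination will be excluded from the PP set". SAP 4.3.2 repeats this clause ("received COVID-19 vaccination within 29 days postvaccination will be excluded from the PP Set") and adds that "Significant protocol deviations will be reviewed and may lead to exclusion from the PP Set". Both documents make the PP Set the basis of the immunogenicity analyses.

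**When a booster is allowed.** Protocol 5.8.2 allows a licensed or authorized COVID-19 booster "per national recommendations, if received after the Day 29 visit". The window row of the Schedule of Events (Protocol 13.1) reads "D–14 to –1 0 NA ±1 ±3 ±3 ±5 ±7". The sixth entry, ±3, belongs to the Day 29 visit, which may therefore be held on Days 26 to 32.

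**How days are counted.** Under SAP Section 4 (General Statistical Considerations), "study day on or after the date of the injection will be calculated as" assessment date minus injection date plus 1. The injection day is thus Day 1, and Day 29 is 28 days later. Neither document says whether the 29 days in the PP clause are study days or elapsed days.

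**The concern.** Permission follows the visit, while exclusion follows a fixed day count. The two agree only if the visit is late enough or the booster is delayed enough. Where they disagree, a participant who did what 5.8.2 allows is treated like one whose titers were contaminated by another vaccine. A vaccine given after a sample cannot have changed that sample, and the same sentence already applies this logic to infection by excluding only later samples.

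At stake are the GMT, GMI and seroresponse summaries. An affected participant would drop out of them at every visit, baseline included, with no scientific reason for the loss.

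**Working it through.** **Inputs.** Day 29 visit on day v, from 26 to 32 (Protocol 13.1). Non-study booster on study day b. 5.8.2 is satisfied if b is later than v, or on the same date but after the visit. The PP clause removes the participant if b ≤ 29 (study-day reading) or b − 1 ≤ 29, that is b ≤ 30 (elapsed-day reading). Sample size, from Protocol 7.2: 30 per dose group, 10% unevaluable, SD 0.45 for the log10 increase.

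**1. The plan's own precision figure.** Evaluable n = 30 × 0.9 = 27. The ratio of the upper 95% limit to the GMI is 10^(t(0.975, n − 1) × 0.45 / √n). For n = 27 this is 10^(2.056 × 0.0866) = 1.507. The plan states 1.5, so the figure reproduces.

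**2. Booster days that 5.8.2 allows and the PP clause penalizes, booster on a later date than the visit.**

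| Visit day | Limit = study Day 29 | Limit = 29 elapsed days (study Day 30) |
|---|---|---|
| 26 | 27, 28, 29 | 27, 28, 29, 30 |
| 27 | 28, 29 | 28, 29, 30 |
| 28 | 29 | 29, 30 |
| 29 | none | 30 |
| 30 to 32 | none | none |
| Pairs | 3 + 2 + 1 = 6 | 4 + 3 + 2 + 1 = 10 |

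**3. Booster later on the date of the visit.** Visit days 26 to 29 give 4 more pairs under the study-day limit. Visit days 26 to 30 give 5 under the elapsed-day limit. An on-time Day 29 visit is thus caught under either reading if the booster follows the same day. Under the elapsed-day reading it is also caught if the booster follows the next day.

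**4. An example.** Visit on Day 26, booster on Day 28. All four scheduled samples (Days 1, 8, 15 and the Day 29 visit) were drawn by Day 26. 5.8.2 is met, yet every result leaves the PP Set. With three secondary assays (neutralizing antibody, S-protein IgG, RBD IgG) that is 4 × 3 = 12 results. Day 85 and Day 180 are not at issue, because footnotes f and k of the schedule stop those immunogenicity draws once a participant has been boosted.

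**5. Cost in precision.** Losses that stay within the planned 3 of 30 leave the ratio at 1.507. One further loss (n = 26) gives 10^(2.060 × 0.0883) = 1.520, and 1.520 / 1.507 = 1.009, about 0.9% wider. Two further losses give 1.534 and three give 1.549. These numbers of losses are assumptions, since the documents give no booster rate.

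**6. After the change proposed below.** With the exclusion tied to the Day 29 visit sample, no pair in steps 2 and 3 is excluded.

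**The case against.** **Day 29 may be meant nominally throughout.** Exclusion criterion 13 and footnotes f and k refer to Day 29 as a day. If 5.8.2 is read the same way, boosters start on Day 30 and the conflict disappears under the study-day limit. Under the elapsed-day limit a Day 30 booster would still be both allowed and penalized. In any case 5.8.2 names the visit, and the visit has a window.

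**The PP sentence is loose.** A lenient reader could carry the limit to later samples over to the vaccination clause. But that clause switches from samples to participants, and the 29-day limit would then have little purpose. If sample-level exclusion is what was meant, the proposed text merely says so.

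**Other provisions could absorb the case.** Criteria 12 and 13 screen out people who at entry plan a licensed vaccine within 4 weeks or a COVID-19 booster by Day 29. That makes the case rare but not impossible: they concern plans held at entry, and Protocol 4.2 says participants will be told of available boosters during the study. A general note in 5.8.2 promises that any effect of other non-study vaccines will be handled in the analysis, and SAP 5.2 says "Major protocol deviations rules will be developed and finalized before database lock". Both leave room for judgment, but neither gives a stated way to restore a participant who committed no deviation and was removed by the set definition.

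**A reader might infer a bias in the other direction.** With a visit on Day 31 or 32 and a booster a day or two earlier, a post-booster titer might seem to stay in and inflate the GMI. The documents do not support making this a finding. Such a booster breaches 5.8.2, and SAP 5.2 lists "Administration of concomitant vaccine(s) forbidden in the protocol" as a major deviation. Footnote k, if its Day 29 is a calendar day, would stop the draw altogether. Nor do the documents give any basis for a size of antibody rise within one or two days of a booster.

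The point about impact stands in full: the effect is close to nil.

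**Conclusion.** The inconsistency is real on the wording, narrow, and minor. In the combinations listed, a participant who complied with 5.8.2 loses valid pre-booster results from the immunogenicity summaries. This rests on reading 5.8.2 as the actual visit date and the PP clause as acting on the whole participant, which is what the words say. The pair counts depend on how the 29 days are counted and do not measure frequency. The case needs a booster unplanned at entry and given within a few days of the visit, so few participants, if any, are likely to be affected.

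It would be wrong to infer that data vanish or that a main conclusion is at risk. The titers remain in the listings for the All Enrolled Set (SAP 8.2.1), the primary safety analysis uses the Safety Set, and the secondary endpoints are descriptive with no hypothesis test. Correcting the clause is optional but worth doing, because the present rule gives the worse result in this case and the correction is cheap.

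**What to change.** In SAP 4.3.2 only, replace the vaccination clause with:

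> Participants who received a non-study COVID-19 vaccine before their Day 29 visit sample are excluded from the PP Set. For participants vaccinated after that sample, results from samples drawn up to the vaccination are retained and results from later samples are excluded. A sample drawn on the same date as the vaccine counts as drawn before it.

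This keeps the existing requirement for a usable Day 29 value and removes the need to decide how 29 days are counted.

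The cost is one extra derivation in the analysis data set and the same-date convention, which is needed because Protocol 5.8.1 requires the date of a vaccination but not its time. The booster dates are already collected. A protocol amendment is not warranted for this alone, since SAP Section 12 says the study was closed early. Because Protocol 7.3 would keep its wording, the difference should be noted in SAP Section 13, which now lists no changes. If the database is already locked, it belongs in the clinical study report.
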